SAR Defined as all noxious and unintended responses to an Investigational Medicinal Product (IMP) related to any dose administered that result in death, are life-threatening, require inpatient hospitalization or prolongation of existing hospitalization, result in persistent or significant disability or incapacity, or are a congenital anomaly or birth defect.

SUSAR A suspected SAR: refers to individual serious adverse event (SAE) case reports from clinical trials where a causal relationship between the SAE and the IMP was suspected by either the Sponsor or the investigator, is not listed in the applicable Reference Safety Information (RSI), and meets one of the following serious criteria: results in death, is life-threatening, requires hospitalization or prolongation of an existing hospitalization, results in persistent or significant disability or incapacity, or is a congenital anomaly or birth defect. All individually reported SARs are considered suspected.

AbbVie will be responsible for SUSAR reporting for the investigational medicinal product (IMP) in accordance with global and local regulatory requirements in participating countries.

Adverse events will be monitored throughout the study to identify any of special interest that may indicate a trend or risk to subjects.

Adverse Event Severity and Relationship to Study Drug

The investigator will rate the severity of each adverse event according to the National Cancer Institute (NCI) Common Terminology Criteria for Adverse Events (CTCAE) version 5.0. If a reported adverse event increases in severity, the initial adverse event should be given an end date and a new adverse event must be reported with a different onset date than the end date of the previous adverse event to reflect the change in severity. The dates of the adverse events cannot overlap.

For adverse events not captured by the NCI CTCAE, the following criteria should be used:

Grade 1	Mild; asymptomatic or mild symptoms; clinical diagnostic observations only; intervention not indicated.
Grade 2	Moderate; minimal, local or noninvasive intervention indicated; limiting age-appropriate instrumental activities of daily living.
Grade 3	Severe or medically significant but not immediately life-threatening; hospitalization or prolongation of hospitalization indicated; disabling; limiting self-care activities of daily living.
Grade 4	Life-threatening consequences; urgent intervention indicated.
Grade 5	Death related to AE.

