9.2.5 Safety Topics of Interest

The safety topics of interest identified using standard MedDRA queries (SMQs) and custom searches are provided in [Appendix B](#).

The incidence of each safety topic of interest will be summarized by SOC and PT. The AEs overview described in Section 9.2.2 and a listing of subject data will be provided for each search.

In addition, for each search, the risk difference for the overall incidence and the corresponding 95% confidence interval (CI) will be computed and displayed in a forest plot and summary table. The risk difference will be defined as the incidence proportion of the navitoclax + ruxolitinib treatment arm minus the incidence proportion of the placebo + ruxolitinib treatment arm. The normal approximation to the binomial distribution will be used to compute the 95% CI.

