Appendix B. Definition of Safety Topics of interest

Safety topics of interest will be identified using the following search criteria:

Safety Topics of Interest	Criteria for Identification of Events
Thrombocytopenia	PTs: 10043554 Thrombocytopenia 10035528 Platelet Count Decreased
Neutropenia	PTs: 10016288 Febrile Neutropenia 10029354 Neutropenia 10029366 Neutrophil Count Decreased
Hemorrhagic Events	SMQ: 20000038 Haemorrhages (Narrow)
Serious Hemorrhagic Events Concurrent ^a with Grade 3 or 4 Thrombocytopenia	SAEs in the Hemorrhagic Events search concurrent with Grade 3 or 4 AE in Thrombocytopenia search
Serious Infections	SAEs in the SOC of Infections and Infestations
Serious Infections with Concurrent ^a with Grade 3 or 4 Neutropenia	SAEs in the Serious Infections search concurrent with Grade 3 or 4 AE in Neutropenia search
Drug-Induced Liver Injury (DILI) ^b	SMQs: 20000006 Drug Related Hepatic Disorders - Comprehensive (Broad) 20000007 Drug Related Hepatic Disorders - Severe Events Only (Narrow)

- a. An AE will be considered concurrent with cytopenia event if the onset date is no more than 7 days prior to the onset of the cytopenia and no more than 7 days after the end of the cytopenia event.
- b. The Drug Related Hepatic Disorders – Comprehensive SMQ (20000006) includes all PTs in the Drug Related Hepatic Disorders - Severe Events Only SMQ (20000007). Summaries will be provided for each SMQ.

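### The SAP's concurrency rule tests only the AE's onset date, so a serious infection or bleed that began more than 7 days before a Grade 3/4 cytopenia and is still ongoing is classed as not concurrent

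*SAP*

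**What the plan says.** SAP Appendix B defines two composite safety topics by concurrency:

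- Bleeding: "SAEs in the Hemorrhagic Events search concurrent with Grade 3 or 4 AE in Thrombocytopenia search".
- Infection: "SAEs in the Serious Infections search concurrent with Grade 3 or 4 AE in Neutropenia search".

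Footnote a supplies the rule for both. Its lower limit is that an event qualifies "if the onset date is no more than 7 days prior to the onset of the cytopenia". Its upper limit, a week beyond resolution of the cytopenia, is worded in the same way. Both limits apply to the onset date of the infection or bleed. Its end date does not appear, and neither document has a clause for an event still ongoing when the cytopenia starts.

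SAP 9.2.5 uses these topics directly: for each search "the risk difference for the overall incidence and the corresponding 95% confidence interval (CI) will be computed", shown in a forest plot and a table.

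Protocol 6.1 sets how onset dates arise. When an event worsens, "the initial adverse event should be given an end date and a new adverse event must be reported with a different onset date". This applies to the cytopenia and to the infection or bleed alike.

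**The concern.** Concurrent ordinarily means present at the same time. The rule asks instead whether the infection or bleed began near or during the cytopenia. For events that began shortly before, or during, the two questions have the same answer. They part for long events. A serious infection already running for more than a week when neutrophils reach Grade 3 is excluded, even if it lasts throughout the neutropenia.

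The rule is also lopsided. It accepts an event that starts 6 days after the cytopenia has ended, with no overlap, and rejects one that covers the whole cytopenia but started 8 days before it. A deliberate tolerance for nearby events explains the first result but not the second.

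These two topics link cytopenia to serious harm, and Protocol 2.2 names thrombocytopenia as the primary dose-limiting toxicity. Scheduled hematology is 4 weeks apart from Week 9 to Week 25 and 12 weeks apart after that (Protocol Appendix D). Extra tests are allowed, but a recorded cytopenia onset can still lag the true onset by more than the 7-day look-back.

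**Working it through.** The plan states no figure to reproduce. The check is to apply the rule literally and compare it with true overlap of dates.

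**Step 1. The rule against overlap.** The rule is: cytopenia onset − 7 ≤ AE onset ≤ cytopenia end + 7. Overlap is: AE onset ≤ cytopenia end and AE end ≥ cytopenia onset. Take an illustrative cytopenia from day 0 to day 14 (assumed dates).

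| AE dates | Footnote a | True overlap |
|---|---|---|
| −20 to +10 | not concurrent | yes |
| −8 to +6 | not concurrent | yes |
| −7 to +3 | concurrent | yes |
| −3 to +5 | concurrent | yes |
| −6 to −2 | concurrent | no |
| −10 to −5 | not concurrent | no |
| +20 to +25 | concurrent | no |

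An ongoing event is missed only if it began more than 7 days before the cytopenia. An already resolved event is counted only if it began 7 days or less before.

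**Step 2. Illustrative size.** Assumptions, none from the documents: AE duration exponential with mean d = 7, 14 or 21 days; cytopenia length L = 7, 14 or 28 days; onset times independent of the cytopenia. In units of days of possible onset:

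- Overlapping events: L (onset during) + d (onset before, still ongoing) = d + L.
- Overlapping but missed: d·exp(−7/d), which is 7 × 0.368 = 2.58, 14 × 0.607 = 8.49 and 21 × 0.717 = 15.05 for d = 7, 14 and 21.
- Miss rate: d·exp(−7/d) / (d + L).

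| | L = 7 | L = 14 | L = 28 |
|---|---|---|---|
| d = 7 | 2.58/14 = 18% | 2.58/21 = 12% | 2.58/35 = 7% |
| d = 14 | 8.49/21 = 40% | 8.49/28 = 30% | 8.49/42 = 20% |
| d = 21 | 15.05/28 = 54% | 15.05/35 = 43% | 15.05/49 = 31% |

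Among events ongoing at cytopenia onset, the share the rule does count is 1 − exp(−7/d): 63%, 39% and 28% for d = 7, 14 and 21.

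**Step 3. Events over before the cytopenia began.** These have measure 7 − d·(1 − exp(−7/d)), which is 2.58, 1.49 and 1.05, out of L + 14 counted. The share runs from 1.05/42 = 2.5% (d = 21, L = 28) to 2.58/21 = 12% (d = 7, L = 7).

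**Step 4. Weight of one subject.** With 230 randomized 1:1, there are about 115 per arm, so one reclassified subject moves that arm's incidence by 1/115 = 0.9 percentage points.

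**The case against.** The strongest defence is that the rule is a deliberate definition. The 7-day allowances are explicit, and an onset-based rule picks out events that arise in or near severe cytopenia, which is a coherent target. An infection that began well over a week earlier arguably did not arise from the neutropenia. This stands for the nearby non-overlapping events: counting them, including those resolved within the look-back, may be intended. It does not justify leaving truly overlapping events out of a topic named for concurrency.

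The illustrative percentages are also open to challenge, and fairly so. Protocol 6.2 calls for dosing to be interrupted for Grade 2 or worse bleeding and for clinically significant infection, which makes a new drug-related cytopenia late in such an event less likely than independence implies. If cytopenia mostly comes first, onsets fall inside the window and the miss rate drops. The rates are also per event, while SAP 9.2 counts a subject once.

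A reader might infer three stronger things that the documents do not support:

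- That every event ongoing at cytopenia onset is missed, or every resolved one counted. Footnote a admits onsets from 0 to 7 days before, so both hold only with the 7-day condition.
- That the severity rule in Protocol 6.1 makes the omission systematically worse. A cytopenia worsening to Grade 3 gets a later onset, which does so; an infection or bleed that worsens also gets a new onset, which can bring it back into the window. The net direction is unknown.
- That missed events vanish from the report. They remain in the broader hemorrhage and serious-infection searches, which have their own risk differences and listings, and in the SAE summaries.

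**Conclusion.** The point holds in its limited form. Footnote a has no clause for an infection or bleed that began more than 7 days before a Grade 3/4 cytopenia and is still ongoing, so such events leave the concurrent topics even when they span the whole cytopenia. This follows from the text alone.

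Its size is unknown. The range of 7% to 54% rests wholly on assumed durations and independent timing, and its upper end should not be read as an estimate. The same rule applies to both arms, but the effect on the risk difference need not cancel if cytopenia frequency differs between them.

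The consequence is confined to two descriptive risk differences under SAP 9.2.5. The primary endpoint and the ranked testing sequence are untouched. This is a worthwhile clarification, not a serious flaw.

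**What to change.** Keep the existing window and add to footnote a: *or if the AE started before and is ongoing at the onset of the cytopenia*. Define ongoing as an AE end date on or after the cytopenia onset date, and treat an AE or cytopenia with no end date as ongoing to data cutoff. Optionally, tabulate separately the AEs that resolved before cytopenia onset, so that a reader can see what the look-back contributes.

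Do not apply the 7-day look-back to the AE's end date. In the model above, the measure of events already over before the cytopenia would rise to 7, from 1.05 to 2.58 now, which enlarges the opposite error.

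The cost is one clause and one date comparison, using dates already collected. The downside is that counts in the two topics may rise. In the same model the rise is d·exp(−7/d) / (L + 14), from 2.58/42 = 6% (d = 7, L = 28) to 15.05/21 = 72% (d = 21, L = 7). The change should be made before unblinding for the analysis.

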Appendix C. Renal and Hepatic Function

Renal function is classified by the baseline creatinine clearance (mL/min) as follows.

Renal Function	CrCL (mL/min)
Normal	≥ 90
Mild Impairment	$60 \leq \text{CrCL} < 90$
Moderate Impairment	$30 \leq \text{CrCL} < 60$
Severe Impairment	$\text{CrCL} < 30$

Creatinine clearance is calculated by the Cockcroft Gault formula.

$$\text{CrCL} = \frac{(140 - \text{Age}) \cdot (\text{Weight in kg}) \cdot [0.85 \text{ if Female}]}{72 \cdot \text{Serum Creatinine (mg/dL)}}$$

Or, if serum creatinine is in $\mu\text{mol/L}$:

$$\text{CrCL} = \frac{(140 - \text{Age}) \cdot (\text{Weight in kg}) \cdot [1.23 \text{ if Male, } 1.04 \text{ if Female}]}{\text{Serum Creatinine } (\mu\text{mol/L})}$$

Hepatic function is classified according to the baseline bilirubin and AST values as follows based on the National Cancer Institute Organ Dysfunction Working Group (NCI-ODWG) definition.⁹

Hepatic Function	Bilirubin (mg/dL)	AST (IU/L)
Normal	$\leq \text{ULN}$	$\leq \text{ULN}$
Mild Impairment	$\leq \text{ULN}$ $> \text{ULN}$ and $\leq 1.5 \times \text{ULN}$	$> \text{ULN}$ Any value
Moderate Impairment	$> 1.5 \times \text{ULN}$ and $\leq 3 \times \text{ULN}$	Any value
Severe Impairment	$> 3 \times \text{ULN}$	Any value

ULN is based on reported values from the lab.
